9.2 SETTING

This retrospective database study will leverage the GE EMR data from October 1, 2013 to April 30, 2018. The EMR consists of patient data from ambulatory care records in the US and is representative of the US population receiving healthcare in the ambulatory setting. Patients will be included in one of three study cohorts based on prescription history from October 1, 2014 to April 30, 2018, allowing for a 12-month pre-index period to describe patient demographic, clinical and treatment characteristics.

Index date

The index date for the nintedanib (or pirfenidone) cohort will be the date of the first nintedanib (or pirfenidone) prescription during the selection window (from October 1, 2014 to April 30, 2018). The index date for the untreated cohort will be the date of the earliest IPF diagnosis or a randomly assigned date between October 1, 2013 and April 30, 2018.

Pre-index period

[figure not shown]
The pre-index period for each cohort will be the 12 months prior to the index date. Patients will be required to have ≥ 1 diagnosis of IPF during the pre-index period (see additional inclusion criteria described below).

Post-index period

The post-index period for each cohort will start from the index date. Since the study aims to evaluate patient characteristics during the pre-index period, no minimum follow-up will be required for post-index period and no study measures will be assess during the post-index period.

Patient selection is illustrated in Figure 1.

Figure 1. Patient Selection

Nintedanib cohort

Inclusion criteria:

- With ≥ 1 diagnosis for IPF (the International Classification of Diseases, Ninth Revision, Clinical Modification [ICD-9-CM] codes 516.3, 516.31, 515,¹¹ or ICD-10-CM codes J84.112) in the EMR between October 1, 2013 to April 30, 2018
- With ≥ 1 prescription for nintedanib between October 1, 2014 and April 30, 2018 (the selection window)
 - The date of the first prescription will be defined as the index date
- With ≥ 1 record in the EMR database during the 12 months prior to the index date (the pre-index period)
- With ≥ 1 diagnosis of IPF during the 12 months prior to the index date
- Age ≥ 40 on the index date
- will explore also requiring ≥ 1 chest CT scan before first IPF diagnosis during the pre-index period¹²

Exclusion criteria:

- With ≥ 1 diagnosis of other known causes of interstitial lung disease (ILD) on the date of or after the first IPF diagnosis during the pre-index period^{12,13}

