- Other known causes of ILD include conditions such as systemic sclerosis, rheumatoid arthritis, systemic lupus erythematosus, dermatomyositis, polymyositis, Sjögren disease, and hypersensitivity pneumonitis (ICD-9-CM codes 135, 237.7, 272.7, 277.3, 277.8, 446.21, 446.4, 495, 500–505, 506.4, 508.1, 508.8, 516.0, 516.1, 516.32–516.37, 516.2, 516.8, 516.9, 517.0, 517.2, 517.8, 518.3, 555, 710.0, 710.0–710.4, 714.0, 714.81, 720, and 759.5, or ICD-10-CM equivalent codes)^{12,13}
- With ≥ 1 prescription for nintedanib prior to the index date
- With ≥ 1 prescription for pirfenidone prior to or on the index date

Pirfenidone cohort

Inclusion criteria:

- With ≥ 1 diagnosis for IPF (ICD-9-CM codes 516.3, 516.31, 515,¹¹ or ICD-10-CM codes J84.112) in the EMR between October 1, 2013 to April 30, 2018
- With ≥ 1 prescription for pirfenidone between October 1, 2014 and April 30, 2018 (the selection window)
 - The date of the first prescription will be defined as the index date
- With ≥ 1 record in the EMR database during the 12 months prior to the index date
- With ≥ 1 diagnosis of IPF during the 12 months prior to the index date
- Age ≥ 40 on the index date
- will explore also requiring ≥ 1 chest CT scan before first IPF diagnosis during the pre-index period¹²

Exclusion criteria:

- With ≥ 1 diagnosis of other known causes of interstitial lung disease (ILD) on the date of or after the first IPF diagnosis during the pre-index period^{12,13}
 - Other known causes of ILD include conditions such as systemic sclerosis, rheumatoid arthritis, systemic lupus erythematosus, dermatomyositis, polymyositis, Sjögren disease, and hypersensitivity pneumonitis (ICD-9-CM codes 135, 237.7, 272.7, 277.3, 277.8, 446.21, 446.4, 495, 500–505, 506.4, 508.1, 508.8, 516.0, 516.1, 516.32–516.37, 516.2, 516.8, 516.9, 517.0, 517.2, 517.8, 518.3, 555, 710.0, 710.0–710.4, 714.0, 714.81, 720, and 759.5, or ICD-10-CM equivalent codes)^{12,13}
- ≥ 1 prescription for pirfenidone prior to the index date
- ≥ 1 prescription for nintedanib prior to or on the index date

Untreated cohort

Inclusion criteria:

- With ≥ 1 diagnosis for IPF (ICD-9-CM codes 516.3, 516.31, 515,¹¹ or ICD-10-CM codes J84.112) in the EMR between October 1, 2013 to April 30, 2018
 - Index date will be defined as the date of the earliest IPF diagnosis or a randomly assigned date based on the exploratory analyses to be performed on the two treatment cohorts (exploring time from IPF diagnosis to treatment initiation)

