 - will explore requiring ≥ 2 diagnoses for IPF that are ≥ 30 days apart to improve the identification of IPF patients^{12,13}
- With ≥ 1 record in the EMR database during the 12 months prior to the index date (the pre-index period)

- Age ≥ 40 on the index date
- will explore also requiring ≥ 1 chest CT scan before first IPF diagnosis during the pre-index period¹²

Exclusion criteria:

- With ≥ 1 diagnosis of other known causes of interstitial lung disease (ILD) on the date of or after the first IPF diagnosis during the pre-index period
 - Other known causes of ILD include conditions such as systemic sclerosis, rheumatoid arthritis, systemic lupus erythematosus, dermatomyositis, polymyositis, Sjögren disease, and hypersensitivity pneumonitis (ICD-9-CM codes 135, 237.7, 272.7, 277.3, 277.8, 446.21, 446.4, 495, 500–505, 506.4, 508.1, 508.8, 516.0, 516.1, 516.32–516.37, 516.2, 516.8, 516.9, 517.0, 517.2, 517.8, 518.3, 555, 710.0, 710.0–710.4, 714.0, 714.81, 720, and 759.5, or ICD-10-CM equivalent codes)^{12,13}
- With prescription for nintedanib or pirfenidone anytime during the data window

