9.3.3 Covariates

The following measures will be evaluated during the 12-month baseline period, including index date, unless otherwise noted. Measures will be reported separately for each of the three cohorts.

For nintedanib and pirfenidone cohorts only:

- Index medication (n, %)
 - Nintedanib
 - Pirfenidone
- Average daily dose of the index prescription
 - Nintedanib (mean, SD, median, min, max) and categories (n, %)
 - 100 mg
 - 150 mg
 - Unknown
 - Pirfenidone (mean, SD, median, min, max) and categories (n, %)
 - 267 mg
 - Unknown
- Time from the earliest diagnosis for IPF to index (mean, SD, median, min, max)
- Prescribing physician specialty (n, %)
 - Primary care
 - Internal medicine
 - Pulmonologist
 - Other

For all cohorts:

Demographic characteristics

- Age (mean, SD, median, min, max) and age categories on index date (n, %)
 - 40-49
 - 50-59

- 60-69
 - ≥ 70
- Gender (n, %)
 - Male
 - Female
- Index year (n, %)
 - 2014
 - 2015
 - 2016
 - 2017
 - 2018
- Region (n, %)
 - Northeast
 - Midwest
 - South
 - West
- Race/ethnicity (n, %) (expected to be missing for about 40% of patients)
 - White
 - African American
 - Hispanic
 - Asian
 - Other
 - Unknown
- Payer type (n, %)
 - Commercial
 - Medicaid
 - Medicare
 - Self-Insured
 - Other/Unknown

Clinical characteristics (based on ICD-9/10-CM procedure and diagnosis codes, laboratory test codes, CPT codes and NDC/RxNorm (to be included in Appendix), as well as other information in the EMR encounter files)

- Body weight (lbs; mean, SD, median, min, max)
 - Body mass index (BMI; kg/m²; mean, SD, median, min, max)
 - BMI category, defined using BMI field (n, %)
 - Underweight ($<18.5 \text{ kg/m}^2$)
 - Normal weight (18.5 to 24.99 kg/m²)
 - Overweight (25 to 29.99 kg/m²)
 - Obese (30 to 34.99 kg/m²)
 - Very obese ($\geq 35 \text{ kg/m}^2$)

- Blood pressure (BP)¹⁴ (n, %)
 - Diastolic BP
 - Normal (<80 mmHg)
 - High (≥ 80 mmHg)
 - Systolic BP
 - Normal (<120 mmHg)
 - Elevated (≥ 120 and < 129 mmHg)
 - High (≥ 130 mmHg), further broken down as follows if data allow
 - Stage 1 (≥ 130 and < 139 mmHg)
 - Stage 2 (≥ 140 mmHg)
- Smoking status at index (n, %); excluding smokeless tobacco; categories to be finalized during analysis
 - Smoker
 - Non-smoker, further broken down as follows if data allow
 - Previous smoker
 - Never smoker
 - Unknown/missing
- Alcohol consumption (n, %)
 - Yes
 - No
 - Unknown/missing

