- Charlson comorbidity index (CCI)¹⁵ (mean, SD, median, min, max) and categories (n, %), defined using ICD diagnosis codes
 - 0
 - 1
 - 2
 - 3
 - 4+
- Respiratory comorbidities¹⁶ (n, %), defined using ICD diagnosis codes
 - COPD (Chronic obstructive pulmonary disease), includes chronic bronchitis and emphysema
 - Pulmonary hypertension
 - Obstructive sleep apnea
 - Lung cancer
 - Pulmonary embolism
 - Asthma
 - Acute respiratory distress syndrome
 - Pulmonary edema
 - Cough
 - Upper respiratory tract infection (includes acute bronchitis)
 - Bronchitis (not specified as acute or chronic)

- Sinusitis
- Gastroesophageal reflux disease (GERD) (n, %), defined using ICD diagnosis codes
- Metabolic disorders¹⁶ (n, %), defined using ICD diagnosis codes
 - Obesity (defined as ICD-9 code 278.0 or ICD-10 code E66 or BMI ≥ 30 kg/m²)
 - Diabetes
 - Any diabetes
 - Type 1 diabetes
 - Type 2 diabetes¹⁶
 - Dyslipidemia (includes hypercholesterolemia and hyperlipidemia)
- Cardiovascular disorders¹⁶ (n, %), defined using ICD diagnosis codes
 - Arrhythmia
 - Atrial fibrillation
 - Heart failure
 - Ischemic heart disease
 - Stroke
 - Hypertension (includes systemic arterial hypertension)
 - Peripheral arterial diseases
 - Cardiomyopathy
- Mental disorders (n, %), defined using ICD diagnosis codes
 - Depression
 - Anxiety
 - Schizophrenia
 - Dementia
 - Bipolar disorders
- Renal impairment (n, %), defined using ICD diagnosis codes
- Hepatic impairment (n, %), defined using ICD diagnosis codes
- Laboratory measures (to the extent that the data allow; tests will be identified by procedure codes and EMR data fields; if repeated measurements of a test are observed, the one closest to the index date will be reported, with the exception of several renal and liver measures (where noted) when any evidence of patient history of the condition during baseline will take precedent over the measure closest to index)
 - Anticoagulation tests (n, %)
 - Prothrombin time (n, %)
 - High (>14 seconds)
 - Normal (10-14 seconds)
 - Low (<10 seconds)
 - Activated partial thromboplastin time (aPTT; n, %)
 - Normal (30-40 seconds)
 - Elevated (41-70 seconds)

- Critical (>70 seconds)
- Bleeding time (n, %)
 - Normal (1-9 minutes)
 - Platelet dysfunction (10-15 minutes)
 - Critical (>15 minutes)
- Hematologic markers
 - Blood hemoglobin (mean, SD, median, min, max)
 - Blood hematocrit (mean, SD, median, min, max)
 - Red blood cell count (mean, SD, median, min, max)
 - Platelet count (n, %)

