- Laboratory values, when recorded (e.g. anticoagulant test, blood counts, kidney and liver function tests)
- Behavioral measures (e.g. smoking status)
- Prescribing physician specialty
- Health insurance details
- Comorbid conditions
- Concomitant medication usage
- Outpatient encounters

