9.7.1 Main analysis

For the primary objective, baseline patient characteristics will be described using descriptive analysis, i.e. described as counts and percentages for categorical variables (e.g. gender, race, comorbidities, treatments, diagnostic tests performed) and measures of central tendency (mean, median, SD, and min/max) for continuous variables (e.g., age, lab measures values, BMI). Differences between the cohorts will be assessed using ASD, where an ASD of at least 10% will be considered a meaningful difference.²² Patients with missing data will be reported as missing and excluded from the comparison for the missing variable.

For continuous variables, the standardized differences will be calculated as

$$d = \frac{(\bar{X}_1 - \bar{X}_2)}{\sqrt{\frac{s_1^2 + s_2^2}{2}}}$$

Where \bar{X} denote sample means in each exposure cohort, and s denotes sample variances.

For categorical variables, the standardized differences will be calculated as

$$d = \frac{(p_1 - p_2)}{\sqrt{\frac{[p_1(1 - p_1) + p_2(1 - p_2)]}{2}}}$$

Where p denotes proportion of a binary baseline variable in the two exposure cohorts.

The confidence intervals (CIs) for standardized differences will also be calculated as defined below:

$$95\% CI = d \pm 1.96 \times \sigma [d]$$

$$\text{where, } \sigma [d] = \sqrt{\frac{n_1 + n_2}{n_1 \times n_2} + \frac{d^2}{2(n_1 + n_2)}},$$

Where n_i denotes sample sizes of each exposure cohort.

Bivariate statistical significance tests such as Chi-square test for categorical variables and Wilcoxon rank sum test or t-test for continuous variables (depending on distribution of data) will also be performed to compare differences in baseline characteristics between the three cohorts. In addition to standardized differences, p-value in comparing characteristics between the three cohorts will also be reported to help identify “key drivers” associated with treatment selection.

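### One EMR record is enough for a 12-month baseline and contact intensity is not a covariate, so differences from the untreated cohort can reflect recording opportunity rather than disease

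*Combined protocol and SAP*

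**What the plan says.** **Entry.** In section 9.2 the untreated list asks for at least one "record in the EMR database during the 12 months prior to the index date (the pre-index period"), and the two treated lists ask for the same: "record in the EMR database during the 12 months prior to the index date". There is no minimum number of visits and no minimum span of prior record. The treated lists add at least one "diagnosis of IPF during the 12 months prior to the index date", which the same visit can satisfy. The untreated list lacks that item, although the general pre-index paragraph of section 9.2 applies it to patients without naming a cohort.

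**Index date.** A treated index is the first prescription on or after October 1, 2014. The untreated index is the "date of the earliest IPF diagnosis or a randomly assigned date", from October 1, 2013, which is also the first day of the data.

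**Covariates.** Section 9.3.3 states: "The following measures will be evaluated during the 12-month baseline period, including index date, unless otherwise noted". Conditions are code-based, for example "Mental disorders (n, %), defined using ICD diagnosis codes". Drug history and procedures are also counts and percentages. Section 9.4 lists "Outpatient encounters" among the key variables available, but section 9.3.3 contains neither an encounter count nor a measure of observation time.

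**Missing data.** Section 9.7.1 says: "Patients with missing data will be reported as missing and excluded from the comparison for the missing variable". Section 9.8 allows unspecified adjustment if systematic patterns of missingness appear.

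**The concern.** A flag built from a code has two states. A patient who has the condition but was never coded for it in the window is counted with those who do not have it. The section 9.7.1 rule cannot help, because nothing is recorded as missing. The share of patients flagged therefore rises with the number of contacts and the length of record, even when true prevalence is the same.

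The ASD and p-value for these characteristics are the primary outcome, and two of the three pairs in section 9.3.2.1 involve the untreated cohort. Section 9.7.1 uses the p-values to identify what drives treatment selection, and section 9.7.1 also lets bivariate significance choose the propensity-model covariates. A recording artefact could therefore be reported as a driver of treatment and then carried into the treated-versus-untreated model.

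**Working it through.** The plan gives no figure to reproduce here: section 9.5 holds feasibility counts only, and visit counts appear nowhere. The check has two parts.

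**1. Is recording opportunity equal as written?**

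| | Treated cohorts | Untreated cohort |
|---|---|---|
| Index is a contact | Yes, a prescription record | Only if the earliest-diagnosis option is used |
| Earliest index | October 1, 2014 | October 1, 2013 |
| Data window before index | At least 12 months | 0 to 12 months if indexed in the first year |
| Pre-index IPF diagnosis | In the cohort's own list | Only in the general paragraph |

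October 2013 to April 2018 is 3 + 48 + 4 = 55 months. If random dates were uniform over that span (an assumption; the plan leaves the distribution to exploratory analysis), 12/55 = 22% would fall where 12 months of baseline cannot be observed. A full data window does not guarantee that a treated patient was in the practice for 12 months either, but the calendar truncation affects the untreated cohort alone.

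**2. How large could the artefact be?**

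Assumptions: the same true prevalence p in both cohorts, probability q that an existing condition is coded at a visit, and v independent visits in the window.

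- Observed prevalence = p × (1 − (1 − q)^v).
- ASD = |p₁ − p₂| / √{[p₁(1 − p₁) + p₂(1 − p₂)] / 2}, the section 9.7.1 formula.

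Worked case, p = 0.30, q = 0.30, 2 versus 4 visits:
- 0.30 × (1 − 0.7²) = 0.153
- 0.30 × (1 − 0.7⁴) = 0.228
- ASD = 0.075 / √[(0.1296 + 0.1760)/2] = 0.075 / 0.391 = 0.192

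With the preliminary sizes of 615 nintedanib and about 10,000 untreated patients, the section 9.7.1 standard error is √[10,615/6,150,000 + 0.192²/(2 × 10,615)] = 0.042. The 95% interval is 0.11 to 0.27, and p < 0.05 would occur with probability 0.997.

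Artificial ASD over the range of assumptions:

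| True prevalence | Visits | q = 0.10 | q = 0.20 | q = 0.30 | q = 0.80 |
|---|---|---|---|---|---|
| 30% | 1 vs 2 | 0.13 | 0.17 | 0.19 | 0.11 |
| 30% | 2 vs 4 | 0.17 | 0.20 | 0.19 | 0.02 |
| 30% | 3 vs 4 | 0.08 | 0.08 | 0.08 | 0.00 |
| 10% | 1 vs 2 | 0.08 | 0.10 | 0.11 | 0.06 |
| 10% | 2 vs 4 | 0.10 | 0.11 | 0.10 | 0.01 |
| 5% | 1 vs 2 | 0.05 | 0.07 | 0.08 | 0.04 |
| 5% | 2 vs 4 | 0.07 | 0.08 | 0.07 | 0.01 |

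At 50% prevalence, 2 versus 4 visits with q = 0.80 gives 0.04. With equal visit counts the model gives 0.00 throughout.

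Put without visits: at a true prevalence of 30%, capturing about 85% of cases in one cohort (25.5% against 30%) is enough to reach an ASD of 0.10. At 10% prevalence, capturing about 72% is enough.

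**The case against.** Several points on the other side stand.

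- **Not every variable is exposed.** Smoking, alcohol and race have unknown categories, and absent laboratory, lung-function and BMI values can be seen as missing. Codes on the index date count for comorbidities; only treatment history excludes that date, and drugs in use at index are tabulated separately. The concern is confined to code-, prescription- and procedure-based flags.
- **The plan is not silent.** Section 9.8 checks for systematic missingness, section 9.9 admits missing and incorrect data, and section 9.7.1 lets face validity choose model covariates. These provisions are generic, and a check for missing values does not detect an absent code.
- **Section 9.2 intends a 12-month look-back**, and ties cohort entry to prescription history from October 2014. The stated range for the untreated index date nevertheless starts a year earlier.
- **The exploratory rules** (two IPF diagnoses at least 30 days apart, a chest CT) address whether the patient has IPF. They do not make the baseline complete.

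Three stronger readings are tempting and are not supported. A reader might infer that untreated patients are in fact seen less and so look healthier; without visit counts, neither the difference nor its direction is known. A reader might infer that the untreated cohort needs no pre-index IPF diagnosis; the general paragraph does require one, so this is an inconsistency rather than a plain omission. A reader might also take 1 − (1 − q)^v itself as the observed prevalence and get ASDs of 0.26 to 0.54 for the same visits with q of 10–30%. That treats every patient in both cohorts as having the condition, which no comorbidity in section 9.3.3 would satisfy.

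**Conclusion.** The concern holds as a risk built into the design, not as a demonstrated difference. One record suffices, absent codes become negatives, no contact-intensity measure is planned, and the untreated index rule allows shorter observable baselines than the treated rule. Nothing comparable separates nintedanib from pirfenidone, whose criteria mirror each other, so the untreated comparisons are the ones mainly at stake.

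Under the stated assumptions, the artefact can pass the plan's 0.10 threshold for common conditions when per-visit coding is incomplete and visit counts differ about two-fold. It sits around the threshold at 10% prevalence, stays below it at 5%, and is below it for 3 versus 4 visits at 30% prevalence. Near-complete coding makes it negligible for 2 versus 4 visits, though not for 1 versus 2 visits at 30% prevalence (0.11). The actual size cannot be computed from the documents, which is the reason to measure contact intensity. This should be changed before analysis.

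**What to change.** 1. Add the number of baseline outpatient encounters and the months from first EMR record to index to section 9.3.3. Report both by cohort and include both in the two propensity models.
2. Because the primary ASDs are unadjusted, the propensity models leave them unchanged. Repeat the primary comparisons as sensitivity analyses: (a) in patients whose first EMR record is at least 12 months before index, which removes untreated index dates before October 2014; and (b) stratified by, or weighted for, encounter count. Both are needed, since a long record does not equalise visit frequency.
3. Reconcile the untreated inclusion list with the general pre-index paragraph on the IPF diagnosis. If the earliest diagnosis is the index, no diagnosis can precede it, so state whether the index date counts.
4. Name differential ascertainment in section 9.9.

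The cost is two derived variables and some extra programming on data already held, with smaller samples in the sensitivity runs only. Encounter count may partly reflect disease severity, so (b) should be read beside the unadjusted result and not in place of it.

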9.12 BIAS

To minimize the bias resulting from treatment switching, study selection for new initiators will be used to exclude patients with nintedanib or pirfenidone use prior to index. In addition, an algorithm for IPF identification adapted from claim-based algorithms (see Section 9.2) will be used for the untreated cohort to minimize the bias resulting from misclassifying patients as having IPF or not.^{12,13}

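### If untreated patients are indexed at their earliest IPF diagnosis, the other-ILD exclusion has an empty window in that cohort but still works in the treated cohorts

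*Combined protocol and SAP*

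**What the plan says.** All the relevant definitions are in Section 9.2 unless noted.

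- **Untreated index date.** "The index date for the untreated cohort will be the date of the earliest IPF diagnosis or a randomly assigned date". The permitted range for that date runs from the start of October 2013 to the end of April 2018. The untreated cohort's own criteria describe the second option as "a randomly assigned date based on the exploratory analyses to be performed on the two treatment cohorts", which will look at time from diagnosis to treatment start. The choice is not made.
- **Treated index date.** "The date of the first prescription will be defined as the index date". Both treated cohorts also need at least one IPF diagnosis in the 12 months before it.
- **Pre-index period.** "The pre-index period for each cohort will be the 12 months prior to the index date", and "The post-index period for each cohort will start from the index date". The same paragraph requires at least one IPF diagnosis in the pre-index period without limiting this to the treated cohorts. The untreated cohort's own list does not repeat that requirement.
- **Other-ILD exclusion.** All three lists remove patients with a diagnosis of "other known causes of interstitial lung disease (ILD) on the date of or after the first IPF diagnosis during the pre-index period".
- **Purpose.** Section 9.12 says that an IPF identification algorithm, set out in Section 9.2, "will be used for the untreated cohort to minimize the bias resulting from misclassifying patients as having IPF or not".

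**The concern.** The exclusion needs two things at once: a code no earlier than the first IPF diagnosis, and a code inside the pre-index period. In the treated cohorts these overlap, because diagnosis comes before the prescription. If the untreated index date is the first diagnosis itself, the overlap disappears.

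The three cohorts would then share the exclusion wording but not its effect. The nintedanib-versus-untreated and pirfenidone-versus-untreated comparisons, and the treated-versus-untreated propensity score, would set cohorts with different effective definitions of IPF against each other. Section 9.7.1 reads differences in characteristics as pointing to what drives treatment choice. Azathioprine, prednisone and other drug use are among the characteristics compared, so a difference created by eligibility could be reported as prescribing behaviour. Nintedanib versus pirfenidone is not affected, because both cohorts are indexed in the same way.

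**Working it through.** The plan gives no figure to reproduce here. The check is date logic, followed by an illustration of size.

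**Step 1: days on which the exclusion can act.** Set the first IPF diagnosis at day 0 and index at day k. An eligible day d must satisfy d ≥ 0, k − 365 ≤ d, and d < k, since the post-index period begins on the index date.

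| Index date | Eligible days, index day outside the window | Eligible days, index day counted |
|---|---|---|
| Earliest IPF diagnosis (k = 0) | 0 | 1 |
| k = 30 | 30 | 31 |
| k = 90 | 90 | 91 |
| k = 180 | 180 | 181 |
| k = 365 | 365 | 366 |

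Treated patients must have a diagnosis before index, so k is at least 1 and the window is never empty. Untreated patients indexed at diagnosis have k = 0.

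**Step 2: other readings of the wording.**
- *Index day counted.* Section 9.3.3 includes the index date in the baseline period for covariates. Borrowing that for eligibility gives one day, so only same-day codes exclude. However, Section 9.2 starts the post-index period on the index date, and the treatment-history heading in Section 9.3.3 leaves the index date out of the pre-index period.
- *The pre-index phrase qualifies only the IPF diagnosis.* A patient indexed at the earliest diagnosis then has no such diagnosis, and the rule has nothing to start from.
- *The general pre-index IPF-diagnosis rule applies strictly.* With k = 0 and the index day outside the window, no untreated patient satisfies it, and the cohort is empty.

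**Step 3: size, under assumptions.** The documents do not say what share of untreated patients carry another-ILD code. Assume a trait with prevalence 30% in IPF and 60% in other-ILD patients, and a share f of other-ILD patients in the cohort. Observed prevalence is p = 0.30(1 − f) + 0.60f. The binary formula in Section 9.7.1 is d = (p₁ − p₂)/√{[p₁(1 − p₁) + p₂(1 − p₂)]/2}.

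| f untreated | f treated | Untreated p | Treated p | ASD |
|---|---|---|---|---|
| 5% | 0% | 31.5% | 30% | 0.015/0.461 = 0.033 |
| 10% | 0% | 33% | 30% | 0.030/0.464 = 0.065 |
| 20% | 0% | 36% | 30% | 0.060/0.469 = 0.128 |
| 20% | 5% | 36% | 31.5% | 0.045/0.472 = 0.095 |

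The result depends on the assumed trait. With 10% versus 40% and an uncontaminated treated cohort, f of 5%, 10% and 20% gives 0.048, 0.094 and 0.179. With 10% versus 70% it gives 0.094, 0.179 and 0.332.

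**The case against.** Four counter-arguments deserve weight.

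1. *The option is undecided.* This stands. If the assigned date falls after the first diagnosis, the exclusion works as it does in the treated cohorts. The index-date paragraph, however, does not say that the assigned date must follow the diagnosis; a date before it would leave the window empty again.
2. *Read strictly, the general rule empties the untreated cohort, so nobody is wrongly kept.* This also stands as a reading. Retention of other-ILD patients follows only if the untreated cohort's own list governs. Either way the index date conflicts with another eligibility rule, and the sections must be reconciled.
3. *The plan has other safeguards.* The two-diagnosis rule (at least 30 days apart) and the chest CT rule are only to be explored, and neither removes a patient for an other-ILD code. The exclusion is the only firm rule that does.
4. *The bias may be small.* This is possible. Several of the scenarios above stay below 0.10.

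A reader might infer that the whole untreated cohort of about 10,000 escapes the exclusion and is therefore contaminated. The documents do not support that: only patients with a qualifying code are affected, their share is not given, and 10,000 is an early feasibility estimate. A reader might also object that patients coded with another ILD only before their first IPF code are kept. That is so in all three cohorts under the same wording, and the plan attributes the rule to cited algorithms. It does not by itself create a difference between cohorts.

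**Conclusion.** The point holds conditionally. Under earliest-diagnosis indexing, with the index day outside the pre-index period as Section 9.2 implies, the exclusion has zero eligible days in the untreated cohort and at least one in every treated patient. Counting the index day rescues same-day codes only. The requirement of a pre-index IPF diagnosis fails for the same reason.

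The direction of the eligibility difference is clear, but its size is not. Whether the 10% threshold is crossed depends on the other-ILD share in the untreated cohort, on how much contamination remains in the treated cohorts, and on how strongly the trait differs between diseases. None of these is in the documents, so the ASD figures are a range under stated assumptions and not an estimate. The option should be closed before programming, because two of the three primary comparisons and one of the two propensity models depend on it.

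**What to change.** Remove the earliest-diagnosis option. Give each untreated patient an index date after the first IPF diagnosis, drawn from the treated cohorts' observed time from diagnosis to first prescription; the exploratory analysis in Section 9.2 already plans to examine that interval. State explicitly that the date must follow the diagnosis. Apply the pre-index IPF-diagnosis rule and one identical other-ILD window to all three cohorts, say whether the index day belongs to that window, and report the number excluded per cohort in the attrition table.

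If earliest-diagnosis indexing is kept, at minimum count other-ILD codes in the 12 months up to and including index in every cohort, and reconcile the pre-index IPF-diagnosis rule with it. State as a limitation that codes entered after the diagnosis date could still exclude treated patients only.

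Extending the exclusion in all cohorts to codes before the first IPF code is secondary and can be a sensitivity analysis.

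The cost is a few sentences in Section 9.2 and a re-run of the attrition table. The untreated cohort would be somewhat smaller, partly because some assigned dates will not satisfy the other eligibility rules; at roughly 10,000 patients before selection it can probably absorb this.
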